7.3. Pharmacokinetics

7.3.1. Serum for Analysis of PF-06730512

Blood samples (approximately 3 mL whole blood) to provide a minimum of 1 mL of serum for pharmacokinetic (PK) analysis will be collected into appropriately labeled tubes at times specified in the [Schedule of Activities](#) section of the protocol.

[figure not shown]
The actual sampling times may change, but the number of samples will remain the same. All efforts will be made to obtain the PK samples at the exact nominal time relative to dosing. However, samples obtained within the time windows specified in the [Schedule of Activity](#) will not be captured as protocol deviations.

In addition to samples collected at the scheduled times, an additional blood sample for determination of PF-06730512 PK may be collected from subjects experiencing unexpected and/or serious AEs. The date and time of the blood sample collection and of the last dosing prior to PK collection will be documented in the CRF.

Samples will be analyzed using a validated analytical method in compliance with Pfizer standard operating procedures (SOPs).

[figure not shown]
The PK samples must be processed and shipped as indicated in the instructions provided to the investigator site to maintain sample integrity. Any deviations from the PK sample handling procedure (eg, sample collection and processing steps, interim storage or shipping conditions), including any actions taken, must be documented and reported to the sponsor. On a case-by-case basis, the sponsor may make a determination as to whether sample integrity has been compromised. Any deviation from the specified sample handling procedure resulting in compromised sample integrity will be considered a protocol deviation.

CCI

7.3.2. Urine for Analysis of PF-06730512

A 20 mL aliquot of the 24-hour urine samples from the Investigational Treatment and Follow-up Periods will be collected. As part of understanding the PK of the investigational product, the samples may be used for evaluation of the bioanalytical method, CCI

CCI

CCI

7.4. Immunogenicity

7.4.1. Immunogenicity Analyses

[figure not shown]
Blood samples (approximately 5 mL) to provide at least 2 mL of serum to detect ADA and NAb against PF-06730512 (~1 mL each for ADA and NAb) will be collected from subjects enrolled at the times specified in the [Schedule of Activities](#). Samples will be analyzed using a validated analytical method in compliance with Pfizer/vendor standard operating procedures (SOPs). Samples determined to be positive for ADA may be further characterized for NAb.

Subjects with positive results at the conclusion of the study may be requested to return for additional follow-up for up to approximately 3 months after the last scheduled follow-up visit. An additional immunogenicity sample will be collected and the information recorded as an unscheduled visit.

The immunogenicity samples must be processed and shipped as indicated in the instructions provided to the investigator site to maintain sample integrity. Any deviations from the immunogenicity sample handling procedure (eg, sample collection and processing steps, interim storage or shipping conditions), including any actions taken, must be documented and reported to the sponsor. On a case-by-case basis, the sponsor may make a determination as to whether sample integrity has been compromised. Any deviation from the specified sample handling procedure resulting in compromised sample integrity will be considered a protocol deviation.

CCI

[figure not shown]
[figure not shown]
biospecimens will be stored for many years (no time limit) to allow for research in the future,
CCI

[figure not shown]
- **CCI**

-

CCI

7.7. Blood Volume

The total blood sampling volume for individual subjects is approximately 560 mL for participating in the study. The blood volumes increase by approximately 72 mL in WOCBP due to serum pregnancy tests; the blood volumes increase by 5 mL in women of non-child-bearing potential due to FSH measurement.

The actual collection times of blood sampling may change, but the total blood volume collected will not increase. Additional blood samples may be taken for safety assessments at times specified by the Sponsor, provided the total volume taken during the study does not exceed 550 mL during any period of 56 consecutive days.

8. ADVERSE EVENT REPORTING

8.1. Requirements

The table below summarizes the requirements for recording safety events on the CRF and for reporting safety events on the Clinical Trial (CT) Serious Adverse Event (SAE) Report Form to Pfizer Safety. These requirements are delineated for 3 types of events: (1) SAEs; (2) non-serious adverse events (AEs); and (3) exposure to the investigational product under study during pregnancy or breastfeeding, and occupational exposure.

Safety Event	Recorded on the CRF	Reported on the CT SAE Report Form to Pfizer Safety Within 24 Hours of Awareness
SAE	All	All
Non-serious AE	All	None
Exposure to the investigational product under study during pregnancy or breastfeeding, and occupational exposure	All (regardless of whether associated with an AE), except occupational exposure	Exposure during pregnancy, exposure via breastfeeding, occupational exposure (regardless of whether associated with an AE)

All observed or volunteered events regardless of treatment group or suspected causal relationship to the investigational product(s) will be reported as described in the following paragraphs.

Events listed in the table above that require reporting to Pfizer Safety on the CT SAE Report Form within 24 hours of awareness of the event by the investigator **are to be reported regardless of whether the event is determined by the investigator to be related to an investigational product under study**. In particular, if the SAE is fatal or life-threatening, notification to Pfizer Safety must be made immediately, irrespective of the extent of available event information. This time frame also applies to additional new (follow-up) information on previously forwarded reports. In the rare situation that the investigator does not become immediately aware of the occurrence of an event, the investigator must report the event within 24 hours after learning of it and document the time of his/her first awareness of the event.

For each event, the investigator must pursue and obtain adequate information both to determine the outcome and to assess whether it meets the criteria for classification as an SAE (see the [Serious Adverse Events](#) section below). In addition, the investigator may be requested by Pfizer Safety to obtain specific follow-up information in an expedited fashion. This information is more detailed than that recorded on the CRF. In general, this will include a description of the event in sufficient detail to allow for a complete medical assessment of the case and independent determination of possible causality. Any information relevant to the event, such as concomitant medications and illnesses, must be provided. In the case of a subject death, a summary of available autopsy findings must be submitted as soon as possible to Pfizer Safety. Any pertinent additional information must be reported on the CT SAE Report Form; additional source documents (eg, medical records, CRF, laboratory data) are to be sent to Pfizer Safety **ONLY** upon request.

As part of ongoing safety reviews conducted by the sponsor, any non-serious AE that is determined by the sponsor to be serious will be reported by the sponsor as an SAE. To assist in the determination of case seriousness, further information may be requested from the investigator to provide clarity and understanding of the event in the context of the clinical study.

8.1.1. Additional Details on Recording Adverse Events on the CRF

All events detailed in the table above will be recorded on the AE page(s) of the CRF. It should be noted that the CT SAE Report Form for reporting of SAE information is not the same as the AE page of the CRF. When the same data are collected, the forms must be completed in a consistent manner. AEs should be recorded using concise medical terminology and the same AE term should be used on both the CRF and the CT SAE Report Form for reporting of SAE information.

8.1.2. Eliciting Adverse Event Information

The investigator is to record on the CRF all directly observed AEs and all AEs spontaneously reported by the study subject. In addition, each study subject will be questioned about the occurrence of AEs in a non-leading manner.

8.1.3. Withdrawal from the Study Due to Adverse Events

Withdrawal due to AEs should be distinguished from withdrawal due to other causes, according to the definition of AE noted below, and recorded on the CRF. Withdrawal from the study due to an adverse event that is related to study drug is done at the discretion of the principal investigator. Notification to the sponsor of the withdrawal must be accomplished immediately. Pregnancy in a study participant must result in immediate cessation of study drug administration.

When a subject withdraws from or is withdrawn from the study because of an SAE, the SAE must be recorded on the CRF and reported, as appropriate, on the CT SAE Report Form, in accordance with the [Requirements](#) section above.

8.1.4. Time Period for Collecting AE/SAE Information

The time period for actively eliciting and collecting AEs and SAEs (“active collection period”) for each subject begins from the time the subject provides informed consent, which is obtained before the subject’s participation in the study (ie, before undergoing any study-related procedure and/or receiving investigational product), through and including a minimum of 70 ± 7 calendar days after the last administration of the investigational product.

For subjects who are screen failures, the active collection period ends when screen failure status is determined.

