All subjects will be required to complete an approximate 8-week Lead-in Period prior to receiving treatment with PF-06730512 in the Investigational Treatment Period. The Investigational Treatment Period will be 24 weeks in duration. Given the rarity of the disease and small sample size of the study, a placebo control is not being used. Adequate safety assessment will be feasible based on data obtained in the study's Lead-in Period in comparison to the Investigational Treatment Period and to historical data from previous clinical studies conducted in FSGS patients.

STUDY OBJECTIVES AND ENDPOINTS

Primary Objective(s):	Primary Endpoint(s):

 To evaluate the efficacy of PF-06730512 compared to baseline in the reduction of proteinuria following 12 weeks of treatment in patients with FSGS. 	
 Percentage change from baseline to Week 13 in Urinary Protein to Creatinine Ratio (UPCR), calculated from the 24-hour urine collection.
Secondary Objective(s):	Secondary Endpoint(s):

 To evaluate the safety and tolerability of PF-06730512 following up to 24 weeks of treatment in subjects with FSGS. To evaluate the effects of PF-06730512 on proteinuria time course. To evaluate the effect of PF-06730512 on renal function. To evaluate the serum exposure of PF-06730512 in FSGS patients. To evaluate the immunogenicity profile of PF-06730512. 	
 Adverse Events, Laboratory Safety Tests (Hematology, Clinical Chemistry, Urinalysis), Body Weight, Blood Pressure, Pulse Rate, Body Temperature and Electrocardiogram (ECG). Percentage change from baseline to Weeks 2, 5, 9, and beyond Week 13, as applicable in UPCR. Percentage change from baseline to Weeks 3, 5, 9, 13 and beyond, as applicable, in estimated glomerular filtration rate (eGFR). Serum concentration of PF-06730512. Incidence of the development of anti-drug antibody (ADA) and neutralizing antibody (NAb).
CCI	

STUDY DESIGN

The adaptive study consists of a Screening Period of up to 43 days, an approximately 8-week Lead-in Period, an Investigational Treatment Period of up to 24 weeks during which subjects will receive PF-06730512 once every 2 weeks (Q2W), followed by a 9-week Follow-up Period.

Subjects in the Lead-in Period will be eligible for transition to active treatment if at Week -1 the UPCR and eGFR meet eligibility criteria, as described in [Section 4.3](#).

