1.3. Rationale

1.3.1. Study Rationale

An “Early Signal of Efficacy” (ESoE) design was chosen to enable the sponsor to relatively quickly identify if PF-06730512 is efficacious in the FSGS patient population prior to expanding the sample size and population to fully demonstrate efficacy and safety that is required for registration. Thus, although the purpose of this phase 2 adaptive study is to evaluate the efficacy, safety, tolerability and pharmacokinetics of PF-06730512 following multiple IV administrations in adult subjects with FSGS, the primary intention is to obtain an early indication of efficacy. Up to 3 doses of PF-06730512 may be assessed in up to 3 separate cohorts.

All subjects will be required to complete an approximately 8-week Lead-in Period prior to receiving treatment with PF-06730512 in the Investigational Treatment Period. The Lead-in Period is designed to:

1. Provide stable baseline data for proteinuria, as measured by urine protein to creatinine ratio (UPCR) and other laboratory and clinical markers of kidney function before subjects receive active treatment, thus enabling potential sensitivity analyses to the primary analysis using internal comparisons.
2. Assist in the interpretation of safety assessments by improving the differentiation of adverse events related to the course of FSGS under standard of care versus adverse events potentially related to investigational product during the Treatment Period.

The Investigational Treatment Period will be 24 weeks in duration.

Given the rarity of the disease and small sample size of the study, a placebo control is not being used. Adequate safety assessment will be feasible based on data obtained in the study’s Lead-in Period in comparison to the Investigational Treatment Period and to historical data from previous clinical studies conducted in FSGS patients.

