6. STUDY PROCEDURES

6.1. Screening and Lead-in Period Activities and Assessments

Subjects will have up to 43 days for Screening procedures to be initiated before the Week -8 Lead-in Period Visit (refer to [Schedule of Activities](#) for details and visit windows). In addition, to prepare for participation into the study, subjects will be instructed on the [Lifestyle Requirements](#), including Contraception Methods ([Section 4.4.2](#)) and Concomitant Treatments ([Section 5.8](#)). In particular, it is important that all prior FSGS treatments are stabilized or discontinued as described in the [Concomitant Treatment\(s\)](#) section of the protocol.

Please also refer to the [Schedule of Activities](#) and [Section 7](#) for details of the study procedures.

A subject may be re-screened, after an agreement has been reached between the investigator and sponsor. If eligibility criteria are not met or evaluable within the Screening or Lead-in window, the subject will be Screen Failed. For subjects who consent to re-screen a new 8-digit study specific subject identification (SSID) number will be assigned and all screening procedures must be repeated. If eligibility confirmation for the Screening or Lead-in Period is delayed due to delayed primary or repeat laboratory results, the subject may enroll once eligibility is confirmed by test results provided the results are received within one week of the specified window.

Screening procedures may be split into 2 or more visits as recommended below. Alternatively, all procedures may be accomplished at one visit, with the exception of FMV and 24-hour urine collection. Subject written informed consent must be obtained prior to any study-specific procedures taking place.

Screening Visit 1

- Obtain informed consent from potential subject;

- Obtain potential subject's medical history, prior and ongoing medication details, demographic information and history of smoking and alcohol consumption);
- A complete history of the subject's FSGS will be collected at screening, including initial diagnosis date, recurrence date if applicable, and prior FSGS treatments administered, as well as capturing any contraindications or intolerance to these medications.

- **CCI**
[REDACTED]

- Review inclusion and exclusion criteria with subject to determine eligibility;
- Review contraceptive use with potential subject;
- Provide subject with container for urine collection and explain the urine collection process;

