6.2. Investigational Treatment Period (Study Weeks 1 to 24)

Refer to the [Schedule of Activities](#) and [Section 7](#) Assessments for the study procedures to be completed during the Investigational Treatment Period. The 24-week Investigational Treatment Period begins in Study Week 1 and continues through Study Week 24, and subjects will receive intravenous treatment with PF-06730512 every other week. In addition, subjects will be reminded on the use of the [Lifestyle Requirements \(Section 4.4\)](#) and [Concomitant Treatment\(s\)](#) of the protocol, in particular, protocol restrictions regarding other FSGS treatments as described in the [Concomitant Treatment\(s\)](#) section of the protocol.

The activities and assessments listed below are to be completed during the Investigational Treatment Period. Please refer to the [Schedule of Activities](#) for visit windows and [Section 7](#) Assessments for the study procedures to be completed during this period.

If an intravenous catheter is placed for serial blood sample collections, ECGs and vital signs (PR, BP) assessments should be either collected prior to the insertion of the catheter or following a sufficient rest period after catheter insertion introduced to minimize impact of catheter placement on these assessments.

Study Week 1 - Day 1

- Review criteria for continuation to the Investigational Treatment Phase, as described in [Section 4.3](#), to confirm eligibility;
- Review concomitant medications;
- Perform a physical exam including body weight and edema assessment;
- **CCI**
- Review contraceptive use with subject;
- Perform serious and non-serious adverse event monitoring;
- Perform single 12-lead ECG pre-dose and at the end of infusion within an approximately 45-minute window;
- Obtain vital signs (sitting single PR, BP and body temperature);
- Collect blood sample for clinical laboratory test, eGFR and fasting lipid profile (subjects must be fasting at least 8 hours prior to blood draw with no food or drink except water);
- Use serum for pregnancy test via test strip as a stat procedure performed locally at the site, in females of child-bearing potential, with the negative result confirmed prior to the administration of investigational product;
- Collect blood sample for pre-dose PK, ADA and NAb, and cytokines (within 30 minutes prior to dosing);
- Enroll the subject via IRT to allocate treatment as described in [Section 5.1](#).
- Intravenously administer PF-06730512 per IP Manual;

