4.3. Safety Analysis Set

The Safety Analysis Set (SAS) is defined as all enrolled subjects who have received at least one dose of study treatment.

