6.6.1. Adverse Events

Listings and summary tables of adverse events will be based on the SAS.

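### Adverse events in subjects who enter the 8-week Lead-in but are never dosed reach no visible SAP output, so the Lead-in safety record comes only from subjects who met the progression criteria and were dosed

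*Protocol*

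**What the plan says.** **Role of the Lead-in.** The Protocol Summary states: "All subjects will be required to complete an approximate 8-week Lead-in Period prior to receiving treatment". It and Protocol 1.3.1 explain that placebo is not used, and that safety will be judged by comparing the Lead-in with the treatment period and with historical FSGS studies. Protocol 1.3.1 gives one purpose of the Lead-in as "improving the differentiation of adverse events related to the course of FSGS under standard of care versus adverse events potentially related to investigational product".

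**Collection.** Under Protocol 8.1.4, AEs and SAEs are collected from consent. For subjects who fail: "For subjects who are screen failures, the active collection period ends when screen failure status is determined". Until then, events go on the CRF (8.1.4.2) and SAEs go to the sponsor's safety group (8.1.4.1).

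**Status of those who do not progress.** Protocol 6.1: "If eligibility criteria are not met or evaluable within the Screening or Lead-in window, the subject will be Screen Failed". Protocol 4.3 sets the criteria for progression (UPCR and eGFR). Withdrawals for other reasons fall under Protocol 6.4 and 8.1.3.

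**Enrolment.** It takes place at Week 1 Day 1, after the Lead-in. Protocol 6.2 tells the site: "Enroll the subject via IRT to allocate treatment as described in" Section 5.1.

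**Analysis population.** SAP 4.3 has the Safety Analysis Set "defined as all enrolled subjects who have received at least one dose of study treatment". SAP 6.6 puts all safety summaries on that set, and SAP 6.6.1 says: "Listings and summary tables of adverse events will be based on the SAS". SAP 4.1 to 4.4 define no set of Lead-in entrants. The disposition text in SAP 6.5.1 names only the efficacy and safety sets and discontinuations by dose.

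**The concern.** Leaving screen failures out of safety tables is usual when screening is only a gate. Here the Lead-in is part of the design: it supplies the internal background record against which on-drug events are read. If that record holds only subjects who later progressed, it is conditioned on what happened during the Lead-in.

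The conditioning is not matched after Day 1. A dosed subject who worsens, even one who stops treatment, stays in the Safety Analysis Set, and SAP 3.4.1 counts follow-up events as treatment emergent. A subject who worsens in the Lead-in far enough to miss the eGFR or UPCR criteria leaves the record altogether. With no drug effect, disease-worsening events could then look rarer before dosing than after it.

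There is also a plain reporting gap. Some subjects need a new renal biopsy only to establish eligibility (Protocol 4.1, 4.2 and 6.1). A complication in someone never dosed would appear in no visible planned output.

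**Working it through.** The plan states no figure on this point, so there is none to reproduce. The check is a trace through the text, then two illustrations on assumed inputs.

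**Trace**

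1. A subject attends Week -8, has an AE, and at Week -1 does not meet Protocol 4.3. Seven weeks of observation have been recorded.
2. Protocol 6.1 makes the subject a screen failure, and 8.1.4 ends active collection.
3. Day 1 enrolment (Protocol 6.2) is never reached and no dose is given.
4. SAP 4.3 requires both enrolment and a dose, so the subject is outside the Safety Analysis Set.
5. SAP 6.6 and 6.6.1 draw every safety summary, AE table and AE listing from that set. The AE is in none of them.

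A subject who withdraws before Day 1 reaches steps 3 to 5 by way of Protocol 6.4 or 8.1.3. SAP 4.3, 6.6 and 6.6.1 are legible, so redaction does not explain the gap.

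**Who is filtered out.** Protocol 4.3 stops subjects whose eGFR falls below its limits, or whose UPCR exceeds 200% of the Week -8 value. It also stops those whose UPCR is 1.5 g/g or lower, or below 30% of the Week -8 value. The filter removes some who worsen and some who improve.

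**Illustration A: the event itself leads to non-dosing.** Assume a constant event rate λ, no drug effect, and a share p of Lead-in events that end in non-dosing. Approximately, for small hazards:

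- Lead-in rate among dosed subjects = λ(1 − p); on-drug rate = λ
- apparent ratio = λ / [λ(1 − p)] = 1/(1 − p)
- p = 0.25: 1/0.75 = 1.33; p = 0.50: 1/0.50 = 2; p = 0.75: 1/0.25 = 4

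The values of p are assumed. The formula applies only to events that lead to non-dosing, not to AEs in general.

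**Illustration B: undosed subjects have a different risk.** Take 22 dosed subjects (the approximate cohort size in the Protocol Summary). Assume a share f of Lead-in entrants is not dosed, with k times the dosed subjects' Lead-in SAE risk.

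- entrants = 22/(1 − f)
- dosed-only rate ÷ all-entrant rate = 1/(1 − f + fk)
- share of events not shown = fk/(1 − f + fk)

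| f | undosed per cohort | k = 1: ratio; not shown | k = 2 | k = 4 |
|---|---|---|---|---|
| 10% | 24.4 − 22 = 2.4 | 1.00; 10% | 0.91; 18% | 0.77; 31% |
| 20% | 27.5 − 22 = 5.5 | 1.00; 20% | 0.83; 33% | 0.62; 50% |
| 30% | 31.4 − 22 = 9.4 | 1.00; 30% | 0.77; 46% | 0.53; 63% |

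The dosed subjects' own risk cancels out. At k = 1 the rate is unbiased, but events are still not shown.

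**The opposite error.** If the extra risk in undosed subjects is a lasting trait, the all-entrant rate is too high a background for the dosed group. At f = 20% and k = 4 it is 1 − 0.20 + 0.20 × 4 = 1.6 times the dosed rate. Set against it, a drug with no effect would show 1/1.6, about 0.62, and a true 1.6-fold increase would show 1.0.

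**The case against.** The case on the other side is substantial, and much of it stands.

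- **Nothing is lost from capture or oversight.** A reader might infer that harms go unreported. The documents do not support that: AEs are on the CRF, SAEs go to the sponsor's safety group and are followed up (Protocol 8.1.4.1 and 8.1.4.2), and safety data are reviewed during the study (9.5 and 9.7). The gap is in the SAP's planned outputs.
- **Not every Lead-in exit is a screen failure.** Protocol 6.1 covers eligibility not met or not evaluable. Withdrawal and loss to follow-up are handled elsewhere, and 8.1.3 requires an SAE leading to withdrawal to be recorded and reported. The exclusion from the Safety Analysis Set is the same.
- **The filter is laboratory-based and two-sided.** A reader might infer that only subjects who stayed well are dosed. Protocol 4.3 also removes marked improvers, allows tests to be repeated, and lets some subjects with reduced eGFR progress on biopsy evidence. An abnormal result is an AE only under the conditions in Protocol 8.2.2. Oedema, infection or thrombosis does not by itself trip a criterion.
- **Review of continuation does not stop at Day 1.** Protocol 4.3 and 5.8.1 require changes in FSGS therapy to be discussed with the sponsor during treatment as well. The asymmetry is narrower: a subject stopped after dosing remains in the Safety Analysis Set, and one stopped before it never enters.
- **The SAP plans no Lead-in versus on-drug rate ratio,** and the protocol pairs the Lead-in with historical data. That limits the harm to a formal comparison, but the comparison the protocol relies on will still be made by readers from these listings.

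These points remove any claim about size and any certainty about direction. They do not supply an output that shows the undosed subjects.

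**Conclusion.** The point holds in this form. Subjects who enter the Lead-in and are never dosed contribute no AE or SAE to any visible SAP table or listing, so the Lead-in record is selected on meeting the progression criteria and being dosed. That matters because the protocol leans on the Lead-in, with historical data, in place of placebo.

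The likely effect is an understated Lead-in rate of disease-worsening events, which makes the drug look worse. A reader might infer that the plan would make the drug look falsely safe; the documents give no ground for that. Nor is the likely direction assured, since marked falls in proteinuria also lead to exclusion.

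The size cannot be computed, because the documents give no Lead-in failure count and no AE rate. A reader might take the ratios of 1.33 to 4 as an estimate of bias. They are an illustration on assumed p, a constant rate and no drug effect, and apply only to events that lead to non-dosing. The range of 0.53 to 1.00 for the dosed-only against the all-entrant rate likewise rests on an assumed 10 to 30% not dosed and 1 to 4 times the risk. The change is worth making because the rule affects the only internal comparator and the data to correct it are already collected.

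**What to change.** - **SAP section 4:** define a Lead-in Safety Set of all subjects who attended the Week -8 visit, dosed or not.
- **SAP 6.6.1, listing:** list AEs and SAEs of all consented but undosed subjects, including biopsy-related events. This must reach back to consent, because an eligibility biopsy may be done during Screening.
- **SAP 6.6.1, table:** summarise Lead-in AEs and SAEs per person-week, from Week -8 to Day 1 or exit, in the Lead-in Safety Set, beside the same table for dosed subjects.
- **SAP 6.5.1:** count Lead-in exits by reason.
- **Interpretation:** state that the two tables are to be read together, because the all-entrant rate may overstate, and the dosed-only rate understate, the background rate for the dosed group.

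The cost is SAP wording, one analysis set, one table, one listing and a set of counts, with no new data collection. The downside is slightly more output and the caveat on interpretation.
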